## 20.0 Potential Benefits to Participants

### 20.1 \* Will participation in this study provide direct benefits to the participant?

☐ Yes ☒ No

## 21.0 Potential Risks to Participants

### 21.1 \* Describe any potential risks: physical, psychological, social, legal or other and assess their likelihood and seriousness. Indicate risks both to the participants and to the embryo or fetus if the participant is or may become pregnant. Please provide the potential risks below:

Blood draw: Potential risks associated with venipuncture include discomfort or pain, ecchymosis, bleeding, nerve damage, phlebitis and infection at the needle insertion site. Additional risks include lightheadedness and a vasovagal response.

Diazepam: Potential risks associated with allergic reaction, drowsiness, loss of coordination, drug/drug interactions with other common medications (antidepressants, other anxiolytics), and alcohol.

Amoxicillin: Potential risk associated with mild to severe allergic reaction, anaphylaxis or hives, nausea, vomiting, and diarrhea (2%). Change in bowel habits and abdominal pain <1%. Vulvovaginal infection (2%). If participant develops vulvovaginal infection she will be given fluconazole course and advised to follow up with gynecology. Participant will not be able to complete last flexible sigmoidoscopy and will be given partial compensation. Antibiotic resistance (negligible). This will not be determined until participant requires another course of amoxicillin and even if he/she develop antibiotic resistance, it will be difficult to know if it was due to the antibiotic course during our study or due to pre-existing antibiotic resistance.

Flexible sigmoidoscopy: Potential risks include intestinal perforation, infection, and bleeding at the biopsy sites.

Privacy Risk: Potential loss of privacy if there is a breach of the RU hospital computer system.

Gene expression: Potentially the participant's identity can be unveiled.

## 22.0 Procedures to Minimize Risks

### 22.1 \* Describe the procedures for protecting against or minimizing any potential risks, and include an assessment of their likely effectiveness. Include a discussion of confidentiality safeguards, where relevant, and arrangements for providing medical treatment, if needed.

The sigmoidoscopy will be performed by an experienced, trained, and credentialed physician.

In the event of a perforation, the participant will be stabilized (placed on a stretcher, the emergency medical response system will be activated, support therapies such as intravenous hydration and oxygen will be provided as needed, vital signs monitored), and the participant will be transferred to the Weill Cornell Emergency Room for further management. The participant's Primary Care Provider will be notified of any change in the participant's medical condition.

Blood draws will be performed by trained professionals using sterile equipment.

Participants will be asked about their medication allergies, current medications and substance use history prior to administering diazepam and amoxicillin.

Participants will be observed for 30-60min after procedure and advised to avoid operating a vehicle and/or heavy machinery for the rest of the day.

Participants who cannot tolerate taking the antibiotic will be assessed by [name] and may be removed from the study. If required, a referral to a primary care physician or clinic will be made.

To minimize the risk of *C.difficile* we have selected a short antibiotic course and we will exclude participants currently receiving chemotherapy or are taking immunosuppressive medications.

If any participant develops *C.difficile* infection and/or vulvovaginal infection, treatment will be prescribed by [name] and participant will be asked to follow up with Primary Care provider.

Participants personal information will be maintained in password protected electronic medical records protected in Rockefeller's network. Access of patient data from remote computer will only be done while in Rockefeller University's VPN.

## 23.0 Alternative Methods or Treatments

**23.1 \* Describe alternative methods or treatments for the disease(s) under study, if any, that were considered and why they will not be used:**

There are no alternative methods or treatments that will allow the investigator to conduct the study.

**24.0 Data and Safety Monitoring**

**This section describes the Data and Safety Monitoring Plan (DSMP) required of each protocol undertaken at the CCTS according to HRPP and NIH policies Notice 98 -084 and Notice 00-038, as cited in Help Sections below. Depending on the level or risk and trial phase, some protocols will need Data and Safety Monitoring Boards.**

**24.1 \* Overall Risk Classification**

**An estimate of risk is necessary to evaluate the adequacy of the planned monitoring. The HELP section provides guidance in making the risk assessment.**

**Read the risk definitions and examples of risk in the HELP section and select the risk category that best describes the current study.**

**If your assessment differs from the definitions the HELP section, describe any factors that modify your judgment of the overall risk in the text box after the risk designation.**

- ☐ MINIMAL RISK  
☐ LOW RISK  
☒ MODERATE RISK  
☐ SIGNIFICANT RISK

Please provide any optional description(s):

**24.2 Protocols Involving Minors**

The chance of direct benefit to the child, or to understanding a disorder not otherwise understood, may be major factors in justifying more than minimal risk in research involving children.

Based on the above definitions, please specify your study's risk classification below:

- ☐ NOT GREATER THAN MINIMAL RISK (the risk of daily life to a healthy child living in a safe environment) 45 CFR 46.404  
☐ GREATER THAN MINIMAL RISK WITH DIRECT BENEFIT TO PARTICIPANT; 45 CFR 46.405  
☐ GREATER THAN MINIMAL RISK, NO DIRECT BENEFIT, BUT BENEFIT TO UNDERSTANDING OF PARTICIPANT'S DISORDER; 45 CFR 46.406  
☐ RESEARCH NOT OTHERWISE APPROVED PRESENTING OPPORTUNITY TO UNDERSTAND, PREVENT OR ALLEVIATE SERIOUS PROBLEM AFFECTING CHILDREN 45 CFR 46.407 (cannot be approved by IRB; requires public comment)

**24.3 DSMB**

1. The NIH requires that all **SIGNIFICANT RISK** protocols have a **Data and Safety Monitoring Board** and provide information about the expertise and independence of that Board
2. Phase III trials require a Data and Safety Monitoring Board,
3. A DSMB may be appropriate for some Phase I and II protocols. (See Help for examples.)
4. It is the investigator's responsibility to report to the IRB, the findings and recommendations of the DSMB as they become available.

Please specify:

- ☐ A DSMB is required for this study
- ☒ A DSMB is not required for this study
- ☐ Unsure

If a DSMB is not required, but is being constituted for other reasons, please explain:

#### 24.4 \* **Safety Review**

Select one:

- ☒ Safety Review is conducted as follows: Laboratory results for research volunteers will be reviewed in a timely manner, usually within 24 hours of receipt by a licensed practitioner. The potential clinical significance of any abnormal finding will be documented in the medical and research record(s), and an appropriate plan or referral developed. The PI's review of safety issues at research team rounds will be documented in the meeting minutes.
- ☐ Protocol Specific

#### 24.5 **Monitoring**

Monitoring Personnel: See Help Bubble to the right.

##### Internal Monitoring

The PI or his/her designee shall conduct internal monitoring to assure the safe and proper conduct of the protocol and all the elements list above in monitoring, following the general principles of quality management. The intensity and frequency of internal monitoring will depend on the protocol risk to participants, the experience of the PI and research team, rate of enrollment, and specific details of the protocol.

Internal monitoring of informed consent and eligibility documentation will be conducted by the research team shortly after enrollment begins. Internal monitoring activities will be documented by logs, meeting minutes or other systematic means.

Specify the research team members who will conduct the internal monitoring of the study (see Help for who may monitor):

##### Internal Monitoring

The PI or his/her designee shall conduct internal monitoring to assure the safe and proper conduct of the protocol and all the elements list above in monitoring, following the general principles of quality management. The intensity and frequency of internal monitoring will

depend on the protocol risk to participants, the experience of the PI and research team, rate of enrollment, and specific details of the protocol.

Internal monitoring of informed consent and eligibility documentation will be conducted by the PI shortly after enrollment begins. Internal monitoring activities will be documented by logs, meeting minutes or other systematic means.

Specify the research team members who will conduct the internal monitoring of the study (see Help for who may monitor):

The PI will be shown how to perform internal monitoring.

For new investigators: Internal monitoring should be conducted at least monthly by new investigators until there are essentially no findings to correct at each review.

#### External Monitoring

\* Is external monitoring planned for this protocol?

- ☐ Yes  
☒ No  
☐ Unsure

If external monitoring is planned, please specify (see Help for who may monitor):

- ☐ (Significant Risk) External monitoring will occur at least every six weeks unless there is no enrollment  
☐ (Moderate Risk) External monitoring will occur at least quarterly  
☐ (Low or Minimal Risk) External monitoring will occur at least annually

If external monitoring is planned, please specify the name of the monitor:

☐ Note that copies of external monitoring reports must be supplied to the IRB and the CRSO as soon as they are made available

Additionally, audits of the research records of minimal, moderate or significant-risk protocols may be performed by the CRSO staff on a random basis or as part of a prospectively identified auditing plan.

## **24.6 Adverse Event Classification**

Adverse events are classified by definition, severity, and association with the investigational trial.

#### Definition of an Adverse Event

Any unfavorable or unintended sign (including abnormal lab findings), symptom or disease temporally associated with the use of a medical treatment or procedure, or protocol, regardless of whether it is considered related to the medical treatment or procedure or protocol.

#### Definition of a Serious Adverse Event

Any unanticipated event that involves the following:

- o results in death
- o is life-threatening
- o requires hospitalization or prolongs existing hospitalization
- o results in persistent or significant disability/incapacity
- o is any medical event which requires treatment to prevent one of the outcomes listed above

Other events can be classified as "serious adverse events" at the discretion of the PI.

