## Definition of Anticipated/Expected Adverse Event

Any adverse event, which has been reported in the Investigator's Brochure, package insert, safety reports, clinical protocol, consent form or listed in the NCI agent-specific Expected Adverse Event List, is classified as an expected adverse event. The investigator must provide the available data of known adverse events and toxicities that have been associated with the study drug, device, intervention, or procedures. This information helps to define the level of risk of the trial and enables safety monitoring. A minimal risk trial may not have any defined risks and a statement to that effect is sufficient to meet the DSMP requirements.

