### Definition of an Unanticipated/Unexpected Adverse Event

Any adverse event that is not consistent with the known, predicted possible effects of the research protocol. An unexpected adverse event varies in nature, intensity or frequency from information on the investigational product provided in the Investigator's Brochure, package insert, safety reports, clinical protocol, or listed in the consent form.

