### 24.7 Reporting Adverse Events

**All AEs will be reported to the IRB at least annually.**

#### Reporting Serious AEs

- ☒ Serious Adverse Events, (SAEs) will be reported to the IRB according to policy, within two working days of identification of the SAE.

Select all that apply:

- ☐ SAEs will be reported to the Sponsor and or ESCROW

SAEs will be reported to the sponsor within how many days of the event?

- ☐ SAEs will be reported directly to the FDA, per 21 CFR 312

SAEs must be reported directly to the FDA within 7 days of the event by the investigator/sponsor.

☐ SAEs will be reported to another entity

Describe:

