#### **Reporting Unanticipated AEs:**

Select all that apply:

☒ UAEs will be reported to the IRB

UAEs that are related and greater than moderate severity must be reported to the IRB according to policy, within two working days of identification of the UAE.

☐ UAEs will be reported to the Sponsor

UAE will be reported to the sponsor within how many days of the event?

☐ UAEs will be reported to the FDA, per 21 CFR 312

UAEs will be reported to the FDA, per 21 CFR 312, within 15 days.

☐ UAEs will be reported to another entity

Describe:

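### The serious adverse event definition admits only unanticipated events, so listed harms such as perforation and anaphylaxis do not trigger mandatory two-day reporting

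*Combined protocol and SAP*

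**What the plan says.** All references are to the combined protocol and SAP.

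- **Seriousness (24.6, Definition of a Serious Adverse Event).** The list of outcomes is introduced by "Any unanticipated event that involves the following". A closing sentence allows the investigator to classify other events as serious at their discretion.
- **Expectedness (24.6).** "Any adverse event, which has been reported in the Investigator's Brochure, package insert, safety reports, clinical protocol, consent form", or in a named external list, "is classified as an expected adverse event". The next definition covers the reverse case: "An unexpected adverse event varies in nature, intensity or frequency from information on the investigational product" given in those same sources. The headings of the two definitions use anticipated and expected, and unanticipated and unexpected, as synonyms.
- **Listed harms (21.1).** For flexible sigmoidoscopy: "Potential risks include intestinal perforation, infection, and bleeding at the biopsy sites". For amoxicillin, the list runs from mild to severe allergic reaction and includes anaphylaxis.
- **Reporting (24.7 and 24.8).** SAEs go to the IRB "within two working days of identification of the SAE". For unanticipated adverse events (UAEs), "UAEs that are related and greater than moderate severity must be reported to the IRB according to policy", also in two working days. Unanticipated problems go to the IRB and the research support office in five working days. All adverse events are reported to the IRB at least once a year.

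**The concern.** Seriousness describes the outcome of an event. Expectedness describes whether the event was foreseen. They are separate classifications, and the SAE definition merges them by making lack of anticipation a condition of being serious. Serious harms that the protocol has already identified are then the ones its mandatory expedited rules do not reach.

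Prompt notice to the IRB matters more here because other independent oversight is thin. The study is rated moderate risk (24.1), no data and safety monitoring board is required (24.3), no external monitoring is planned, and internal monitoring rests with the investigator (24.5). Section 25.1 gives criteria for individual participants but no study-level pause rule tied to serious events. The participants are healthy volunteers (17.4) with no direct benefit (20.1), and each completer has three sigmoidoscopies with up to 20 biopsies at each (12.9, Visits 2, 4 and 5).

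**Working it through.** The plan gives no figure to reproduce. The check follows one event through the definitions and then through every reporting route.

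**Event: a perforation that leads to hospitalization.**

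1. *Adverse event?* Yes, under the general definition in 24.6.
2. *Expected?* Yes. It is named in 21.1, and an event reported in the clinical protocol counts as expected. Section 22.1 plans stabilization and emergency room transfer for a perforation, so it is foreseen at a serious level and not only by name.
3. *SAE?* No. Hospitalization is a listed outcome, but the event is not unanticipated. The two-working-day SAE rule in 24.7 is not triggered.
4. *UAE?* No, because it is expected. The two-working-day UAE rule in 24.7 is not triggered.
5. *Unanticipated problem?* No. All three criteria in 24.6 must be met, and the first is that the event was not expected from the study documents. The five-working-day rule in 24.8 is not triggered.
6. *What is left?* At-least-annual reporting of all adverse events (24.7), plus the investigator's option to classify the event as serious.

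**The other listed harms.**

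| Harm | How the protocol foresees it | Mandatory expedited route? |
|---|---|---|
| Perforation | Named in 21.1; emergency transfer planned in 22.1 | None |
| Severe allergic reaction or anaphylaxis, amoxicillin | Named in 21.1 with severity stated | None |
| Anaphylactic shock, diazepam | Emergency management and transfer described in 25.1 | None |
| Biopsy-site bleeding, infection | Named in 21.1 with no severity or frequency | Arguable |

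The last row is open because the definition of an unexpected event includes a difference in intensity. A bleed or infection needing hospitalization could be called more intense than what 21.1 lists. It would then be unanticipated, hence an SAE and, if related and of sufficient severity, a reportable UAE.

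**Exposure.** Evaluable participants (13.6) × sigmoidoscopies per completer (12.9) = 10 × 3 = 30 procedures. Up to 20 people may sign consent (13.7), and participants who cannot tolerate at least five days of antibiotic are replaced (12.9, Visit 4). The actual number could therefore exceed 30, with a ceiling of 20 × 3 = 60 if everyone who consented completed all three.

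**The case against.** Several points on the other side have force.

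- **Investigator discretion.** The investigator may classify a perforation as serious and report it in two working days. This stands, so it would be wrong to say that listed harms escape two-day reporting altogether. The sentence is permissive, however, and leaves the decision to the person running the study.
- **Intensity.** A reader might infer that every serious risk in 21.1 falls outside the definition. The documents do not support that, because bleeding and infection are listed without severity and a serious case could be classed as unexpected. The argument does not rescue perforation or anaphylaxis, which the protocol foresees at a serious level.
- **IRB policy.** Section 24.7 says that reporting follows policy. That policy is not in the documents and may be broader. This limits the finding to the protocol's own text. If the policy is broader, the protocol's definition is out of line with it and still needs correction.
- **Little remaining exposure.** Enrollment closed on May 24, 2024 (note at the end of 12.9), and no new consents (13.8) or visits (14.1) are projected for the next year. The 30 procedures should not be read as risk still to come.
- **Limited downstream effect.** All adverse events are still graded under CTCAE v5.0 (24.6) and reported at least annually, no SAE analysis is planned in 12.10, and the emergency response to a perforation in 22.1 does not depend on its classification. This is right, and it keeps the point to timely independent review and complete harm reporting.
- **Form text.** The wording may come from an institutional template. That is an inference, and the text is in any case the operative rule of this protocol.

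**Conclusion.** The concern holds for harms that the protocol foresees at a serious level: clearly perforation and severe allergic reaction or anaphylaxis, and only arguably bleeding and infection. For these, none of the three mandatory expedited routes applies. The required limit moves from two working days to at-least-annual reporting. Twelve months is the outer limit of that rule, not an expected delay.

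This rests on two conditions: that the investigator does not use the optional discretion, and that the IRB policy cited in 24.7 is no broader than the protocol text. It also takes anticipated and expected as the same term, as the headings in 24.6 do.

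A reader might infer that a serious event has already gone unreported or that the SAE count is too low. The documents show neither. An undercount is possible under the written rule but not demonstrated. The primary outcome and its paired analysis (12.7, 12.10) are not affected. The definition is worth correcting because the stated rule gives the wrong result for foreseeable serious harms; most of the remaining benefit is retrospective.

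**What to change.** In 24.6, replace the opening words of the SAE definition with: *Any adverse event, whether or not anticipated, that involves the following.* Keep the two expectedness definitions as they are, and use them only for the UAE rule in 24.7 and the unanticipated-problem rule in 24.8. Confirm that the result agrees with the IRB policy that 24.7 cites.

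Because enrollment is closed, also re-check every logged adverse event against the corrected definition. Report to the IRB any event reclassified as serious, and use the corrected count in any report of harms.

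The cost is one phrase in an amendment and a short review of a small log. If the wording is institutional form text, the study team may need to agree the change with the office that owns the form.

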## Definition of Anticipated/Expected Adverse Event

Any adverse event, which has been reported in the Investigator's Brochure, package insert, safety reports, clinical protocol, consent form or listed in the NCI agent-specific Expected Adverse Event List, is classified as an expected adverse event. The investigator must provide the available data of known adverse events and toxicities that have been associated with the study drug, device, intervention, or procedures. This information helps to define the level of risk of the trial and enables safety monitoring. A minimal risk trial may not have any defined risks and a statement to that effect is sufficient to meet the DSMP requirements.

### Definition of an Unanticipated/Unexpected Adverse Event

Any adverse event that is not consistent with the known, predicted possible effects of the research protocol. An unexpected adverse event varies in nature, intensity or frequency from information on the investigational product provided in the Investigator's Brochure, package insert, safety reports, clinical protocol, or listed in the consent form.

### Definition of an Unanticipated Problem (UaP)

A UaP is an event or circumstance that meets all the following three criteria: [1] the nature, severity, frequency of the event(s) or information was not expected in the descriptions in the study documents or the characteristics of the participant population being studied; [2] there is a reasonable possibility that the procedures involved in the research caused or are linked in a significant way to the problem; [3] the event or information suggests that the research places participants or others at a greater risk of harm than was previously known or recognized (including physical, psychological, economic, or social harm).

